8.4.4 Pregnancy Losses

The following terminology should be used for reporting of pregnancy losses during the trial:

Biochemical pregnancy: Positive βhCG test but no gestational sac is observed on later

transvaginal ultrasound, or menstruation is reported

Spontaneous abortion: Positive \(\beta \) HCG test but all intrauterine gestational sacs are

without fetal heart beat as documented by ultrasound, or there

are no viable fetuses observed by ultrasound

Vanishing twin: Spontaneous disappearance of at least one intrauterine

gestational sac with or without heart beat in a pregnancy where one viable fetus remains as documented by ultrasound

Menotrophin HP, FE 999906, FE 999911 Solution for Injection Clinical Trial Protocol Trial Code: 000303 Date: 14 Oct 2019 E-Study Protocol-21539; Ver. 6.0

Supersedes: 5.0 Page 75 of 103

Ectopic pregnancy: Extrauterine gestational sac with or without fetal heart beat as

documented by ultrasound or surgery

Concerning timing, a pregnancy loss occurring before ongoing pregnancy (i.e. a positive β hCG tests but no ongoing pregnancy at 8-9 weeks after blastocyst transfer) will be defined as an early pregnancy loss, while a pregnancy loss occurring after ongoing pregnancy (i.e. at least 1 intrauterine viable fetus at 8-9 weeks after blastocyst transfer but no live birth) during the post-trial follow-up will be defined as a late pregnancy loss.

8.4.5 Multiple Pregnancies

Multi-fetal gestations are not to be reported as adverse events.

Trial Code: 000303

Date: 14 Oct 2019 E-Study Protocol-21539; Ver. 6.0 Supersedes: 5.0 Page 76 of 103

8.5 Serious Adverse Events

8.5.1 Serious Adverse Event Definition

Serious Adverse Events during the Trial

An event is defined a serious adverse event (SAE) if it:	Guidance							
results in death	Any event resulting in a fatal outcome must be fully documented and reported, including deaths occurring within four weeks after the treatment ends and irrespective of the causal relationship to the IMP. The death of a subject enrolled in a trial is per se not an event, but an outcome.							
is life-threatening	The term life-threatening refers to an adverse event in which the subject wat immediate risk of death at the time of the event. It does not refer to an event, which may have caused death if it were more severe.							
requires in-patient hospitalization or prolongation of existing hospitalization	The term hospitalization means that the subject was admitted to hospital or that existing hospitalization was extended as a result of an event. Hospitalization describes a period of at least 24 hours. Over-night stay for observation, stay at emergency room or treatment on an out-patient basis d not constitute a hospitalization. However, medical judgement must always be exercised and when in doubt the case should be considered serious (i.e. case fulfils the criterion for a medically important event). Hospitalizations for administrative or social purposes do not constitute an SAE. Hospital admissions and/or surgical operations planned before trial inclusion are no considered adverse events, if the illness or disease existed before the subject was enrolled in the trial, provided that the condition did not deteriorate during the trial.							
results in persistent or significant disability/incapacity	Disability/incapacity means a substantial disruption of a person's ability to conduct normal life functions. In doubt, the decision should be left to medical judgement by the investigator.							
is an important medical event	Medical and scientific judgment should be exercised in deciding whether other situations should be considered serious such as important medical events that might not be immediately life-threatening or result in death or hospitalization but might jeopardize the patient or might require interventio to prevent one of the other outcomes listed in the definition above. Example of such events are intensive treatment in an emergency room or at home for allergic bronchospasm, blood dyscrasias or convulsions that do not result in hospitalization, or development of drug dependency or drug abuse.							

Supersedes: 5.0 Page 77 of 103

Elective Termination in the Time between Clinical and Ongoing Pregnancy

In connection with elective termination due to a congenital anomaly observed at or after the clinical pregnancy visit (i.e. 5-6 weeks after transfer), but before ongoing pregnancy has been established (i.e. 8-9 weeks after transfer), the congenital anomaly of the fetus should be reported as a SAE.

The congenital anomaly leading to elective termination will be coded using both MedDRA and ICD-10 and classified as minor or major.^c

Serious Adverse Events during Post-trial Activities

Pregnancy outcome and neonatal health data (i.e. gestational age, gender, birth weight and length, and Apgar scores after 1, 5 and 10 minutes) will be gathered for all subjects with an ongoing pregnancy. These data will be collected at birth. In addition, data on neonatal SAEs will be collected at 4 weeks and minimum 6 months after birth. These data will be reported separately.

The following untoward medical occurrences reported as part of this post-trial follow-up information will be recorded as SAEs:

- Death of mother in connection with pregnancy or labor
- Death of neonate / infant
- Stillbirth^d
- Neonate admitted to the neonatal intensive care unit (NICU) regardless of duration, or neonate / infant admitted to the neonatal care unit (NCU) / pediatric care unit (PCU) for more than 2 hours
- Congenital anomaly / birth defect
- Medically important event

In case of admission to NICU or NCU / PCU, the reason for admission must be reported as an SAE, rather than just the act of hospitalization.

Congenital anomalies will be coded by Ferring using both MedDRA and ICD-10 and classified as minor or major.

^c Major abnormalities: a life threatening structural anomaly or one likely to cause significant impairment of health or functional capacity and which needs medical or surgical treatment.

Minor anomalies: relatively frequent structural anomaly not likely to cause any medical or cosmetic problems.

^d Stillbirth: ≥ gestational age 24 weeks + 0 days, calculated from the day of transfer + 19 days

Supersedes: 5.0 Page 78 of 103

8.5.2 Collection, Recording and Reporting of Serious Adverse Events

[figure not shown]
SAE Reporting by the Investigator

All SAEs must be reported **immediately** to Ferring Pharmacovigilance as soon as it becomes known to the investigator and not later than within 24 hours of their knowledge of the occurrence of an SAE.

The investigator is responsible for submitting the completed SAE Report Form with the fullest possible details within 3 calendar days of his/her knowledge of the SAE.

SAE Report Form

The SAE Report Form is included in the e-CRF system, and must be completed and submitted according to the instructions provided on the form. In case the e-CRF cannot be accessed and hence the SAE Report Form cannot be filled in within the e-CRF system, a paper SAE Report Form should be used and sent to Ferring Pharmacovigilance using the contact details below.

Completion of the Demographics, Adverse Event Log, Medical History Log and Concomitant Medication Log are mandatory for initial reports and for follow-up reports if any relevant changes have been made since the initial report. Data entries must have been made in the e-CRF for Ferring Pharmacovigilance to access the information.

Additional information relevant to the SAE such as hospital records, results from investigations, e.g. laboratory parameters (that are not already uploaded in the e-CRF), invasive procedures, scans and x-rays, and autopsy results can be faxed or scanned and e-mailed to Ferring Pharmacovigilance using the contact details in the section above. In any case this information must be supplied by the investigator upon request from Ferring. On any copies provided, such details such as subject's name, address, and hospital ID number should be concealed and instead subject number should be provided.

The investigator will supply Ferring and the IRB with any additional requested information such as results of post-mortem examinations and hospital records.

Overdose and medication errors of IMP with and without clinical consequences will be tracked in the e-CRF and reviewed by Ferring Pharmacovigilance on an ongoing basis.

Ferring will report SAEs according to local regulations.

Supersedes: 5.0 Page 79 of 103

8.6 Follow-up of Adverse Events and Serious Adverse Events

8.6.1 Follow-up of Adverse Events with Onset during the Trial

During the trial, the investigator must follow-up on each adverse event until it is resolved or until the medical condition of the subject is stable.

After the subject's last visit, the investigator must follow-up on any adverse event classified as serious or considered to have a reasonable possible causality to the IMP until it is resolved or until the medical condition of the subject is stable. All such relevant follow-up information must be reported to Ferring. Follow-up should continue until the outcome of recovered, recovered with sequelae or fatal, has been reached. Further, if the event is a chronic condition, the investigator and Ferring may agree that further follow-up is not required.

8.6.2 Follow-up of Serious Adverse Events with Onset during the Post-Trial

For post-trial SAEs in neonates, where the neonate has not recovered at the 6 month follow-up assessment, the investigator must follow up until the SAE has resolved. If the SAE is a chronic condition or the medical condition of the neonate is stable, the investigator and Ferring may agree that further follow-up is not required.

8.6.3 Collection of Serious Adverse Events with Onset after End-of-trial

If an investigator becomes aware of an SAE after the subject's last visit in the trial, and he/she assesses the SAE to have a reasonable possible causality to the IMP, the case will have to be reported to Ferring Pharmacovigilance, regardless how long after the end of the trial this takes place.

Supersedes: 5.0 Page 80 of 103

9 STATISTICAL METHODS

This section details the planned statistical analyses for the primary endpoint and outlines the analysis plan for the secondary endpoints. All analyses and further descriptions of the statistical methodology for the primary and secondary endpoints will be included in the Statistical Analysis Plan (SAP). The SAP will be available before breaking the blind. A separate SAP will be prepared to cover the post-trial information.

9.1 Determination of Sample Size

The present trial is a pharmacodynamic comparison of a marketed product to a new formulation of the same. With 188 subjects per treatment group, the trial has at least 85% power to demonstrate the non-inferiority of MENOPUR liquid to MENOPUR powder in the number of fertilized oocytes at the 1-sided significance level of 0.025. This is based on the results for MENOPUR powder from the COMBINE trial conducted in a similar setting (GnRH agonist protocol, MENOPUR starting dose of 225 IU for the first five days, insemination by ICSI etc.) and in a similar population (infertile women between 18 and 42 years). The mean (SD) of the number of fertilized oocytes were 7.88 (5.15) with similar results in the two age groups (7.92 in the <35 years age group vs. 7.80 in the ≥35 years age group). The non-inferiority margin of -1.60 will retain 80% of the expected comparator effect.

After adjusting for 5% missing data, approximately 400 subjects will be randomized (1:1) into this trial, stratified by trial site and age (<35years and ≥35 years).

A blinded sample size reassessment will be done when data on the primary endpoint are available for 70% of the planned subjects or when 300 subjects are randomized, whichever comes first. The sample size reassessment will be done without breaking the blind and without inflating the type I error of the trial, in line with current regulatory guidelines. The expected maximum number of subjects to be randomized is 500 (250 subjects per treatment group), corresponding to a blinded one-sample (both groups pooled) standard deviation estimate of 5.8 and 85% power.

9.2 Subject Disposition

The number and percentage of subjects within each analysis set, randomized subjects treated with IMP (MENOPUR liquid including Placebo to MENOPUR powder or MENOPUR powder including Placebo to MENOPUR liquid), and subjects prematurely discontinued from the trial will be summarized. All post-baseline discontinuations will be summarized by reason for discontinuation. The number of subjects screened and not randomized will be presented.

9.3 Protocol Deviations

The rating of protocol deviations as 'minor' and 'major', as well as the criteria for major protocol deviations with the implication of exclusions from the per-protocol analysis set will be decided by

Supersedes: 5.0 Page 81 of 103

the Ferring clinical team on the basis of a blinded review of data before declaration of clean file and lock of database.

The list of major protocol deviations will be detailed and documented in the clean file document prior to database release. Major protocol deviations will be summarized and listed by subject.

9.4 Analysis Sets

9.4.1 Intention-to-Treat Analysis Set

The intention-to-treat (ITT) analysis set comprises all randomized (as planned) subjects.

9.4.2 Modified Intention-to-Treat Analysis Set

The modified intention-to-treat (mITT) analysis set comprises all randomized (as planned) subjects who received at least 1 dose of IMP (MENOPUR liquid including Placebo to MENOPUR powder or MENOPUR powder including Placebo to MENOPUR liquid).

9.4.3 Per Protocol Analysis Set

The per protocol (PP) analysis set comprises all mITT subjects except those excluded as a result of major protocol deviations.

9.4.4 Safety Analysis Set

The safety analysis set comprises all treated subjects and is analyzed according to the actual treatment received.

9.5 Trial Population

9.5.1 Demographics and other Baseline Characteristics

Descriptive statistics of demographics and other baseline characteristics will be presented for the subjects in the mITT, PP, and safety analysis sets by treatment group, separately.

9.5.2 Medical History, Concomitant Medication and Other Population Characteristics

All medical history will be coded using MedDRA. The version of MedDRA will be documented. Medical history will be listed by subject and summarized for each medical item.

Concomitant medications will be coded using the World Health Organization Drug Reference List. Prior and concomitant medications will be summarized by Anatomical Therapeutic Chemical classification first level (alphabetically) and Anatomical Therapeutic Chemical classification second level (in decreasing order of frequency).

Supersedes: 5.0 Page 82 of 103

Infertility history, menstrual history and reproductive history will be listed by subject and presented in summary tables.

9.6 Efficacy Endpoint Assessments

9.6.1 General Considerations

All primary and secondary efficacy analyses will be conducted for the mITT analysis set. Furthermore, sensitivity analyses will be conducted for the PP and ITT analysis sets as appropriate.

Continuous variables will be described with the number of non-missing values, mean, standard deviation, median, and minimum/maximum values. Categorical variables will be described with the number and percentage of subjects with each level. Missing values will not be included in the calculation of percentages unless otherwise specified. All individual subject data will be listed.

9.6.2 Primary Endpoint

The primary objective of the trial is to demonstrate the non-inferiority of MENOPUR liquid versus MENOPUR powder with respect to the number of fertilized oocytes in women undergoing controlled ovarian stimulation powder. The non-inferiority limit for the difference between treatments (MENOPUR liquid minus MENOPUR powder) is set as -1.60. The non-inferiority hypothesis to be tested for the primary endpoint will be:

H₀: $\mu_{MENOPUR}$ liquid - $\mu_{MENOPUR}$ powder ≤ -1.60

against the alternative

H₁: $\mu_{\text{MENOPUR liquid}}$ - $\mu_{\text{MENOPUR powder}} > -1.60$

where $\mu_{MENOPUR\ liquid}$ and $\mu_{MENOPUR\ powder}$ denote the mean numbers of fertilized oocytes in subjects treated with MENOPUR liquid and MENOPUR powder, respectively.

The null hypothesis (H₀) will be tested against the alternative by constructing a 2-sided 95% confidence interval for the difference in the least squares mean number of fertilized oocytes between the two treatment groups. If the lower-limit of the 95% confidence interval is greater than the non-inferiority limit (-1.60), the null hypothesis will be rejected and it will be claimed that MENOPUR liquid is non-inferior to MENOPUR powder with respect to the number of fertilized oocytes.

Due to the expected large sample size, the primary endpoint will be analyzed using a mixed effects two-way analysis of variance (ANOVA) model, based on the asymptotic normal approximation. The model will include the treatment group and the age group as fixed factors, as well as the trial site as a random effect. The least squares mean estimate of the treatment difference in the number of fertilized oocytes and the associated 95% confidence interval will be derived through an

Trial Code: 000303

Date: 14 Oct 2019
E-Study Protocol-21539; Ver. 6.0
Supersedes: 5.0
Page 83 of 103

LSMEANS statement in the SAS PROC GLM procedure. For subjects who do not have any oocytes retrieved, or do not have fertilization assessment due to early withdrawal, or any other reason, the number of fertilized oocytes will be considered as zero.

If the 95% confidence interval for the treatment difference not only lies above the non-inferiority limit (-1.60) but also above zero then there is evidence of superiority in terms of statistical significance at the 2-sided 5% level. With evidence of superiority, the corresponding 2-sided p-value will be reported. There is no need for a multiplicity adjustment since it is a simple closed test procedure.

The primary efficacy analysis will be conducted for the mITT population. Sensitivity analyses for the primary endpoint will be conducted for both the ITT analysis set and the PP analysis set.

9.6.3 Secondary Endpoints

All secondary efficacy endpoints will be summarized using tables and figures, as appropriate. Additional details will be specified in the Statistical Analysis Plan. The secondary efficacy endpoints include:

- Positive βhCG rate, clinical pregnancy rate and ongoing pregnancy rate will be presented by descriptive statistics by treatment group.
- Early pregnancy loss will be presented by descriptive statistics by treatment group.
- The follicle cohort on stimulation day 6 and last day of stimulation will be summarized by treatment on the follicle level (number of follicles ≤9 mm, 10-11 mm, 12-14 mm, 15-16 mm, and ≥17 mm) and subject level (largest follicle size and average number of follicles ≥17 mm, ≥15 mm, and ≥12 mm). Tables will be produced for all subjects and for subjects with oocytes retrieved.
- The endocrine profile will be summarized using descriptive statistics by scheduled visit, as well as for the change from baseline, if appropriate. The analyses will be based on the central laboratory values.
- The number of oocytes retrieved, the number of metaphase II oocytes, and the number of oocytes undergoing ICSI will be summarized by frequency distribution and by descriptive statistics for each treatment group.
- The fertilization rate will be expressed as a percentage for each subject and calculated as 100 times the ratio of the number of fertilized 2PN oocytes to the number of oocytes retrieved. Descriptive statistics will be provided by treatment group.

Supersedes: 5.0 Page 84 of 103

• The number and quality of blastocysts 5 days after oocyte retrieval will be summarized by frequency distribution and by descriptive statistics for each treatment group.

Based on the serum FSH concentrations, a population pharmacokinetic model will be developed. The modelling will be detailed in a modelling analysis plan and reported separately.

9.7 Extent of Exposure and Treatment Compliance

The number of days exposed and the total amount of IMP and NIMP administered will be summarized and listed per subject and treatment. Subjects that deviate from the planned treatment will also be listed.

9.8 Safety

9.8.1 General Considerations

Analyses for the safety analysis set will be conducted according to the actual treatment received.

Missing values will be treated as missing, except for causality, intensity, seriousness, and outcome of adverse events. A worst-case approach will be used: if causality is missing, the adverse event will be regarded as related to the IMP; if the intensity of an adverse event is missing, the adverse event will be regarded as severe; if seriousness is missing, the adverse event will be regarded as serious; if outcome is missing, and no date of outcome is present, the outcome is regarded as 'ongoing'.

Data will be presented by summary tables and listings only. Categorical data will be summarized by treatment using the number and percentage of subjects in each category. For calculation of percentages, the denominator will be the total number of subjects in the respective treatment group in the safety analysis set. Continuous data will be summarized by treatment using number, mean, standard deviation, median, minimum, and maximum.

All individual subject data will be listed per subject and treatment as observed including any derived values.

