In subjects with a negative pre-dosing sample, a treatment-induced anti-MENOPUR antibody response will be defined as any post-dosing sample being positive in the confirmatory assay (i.e. assay 2).

In subjects with a positive pre-dosing sample, a treatment-induced anti-MENOPUR antibody response will be defined as a statistically determined fold increase in titers from the pre-dosing assessment to a post-dosing assessment.^a

A subject is defined to have treatment-induced anti-MENOPUR antibodies with neutralizing capacity, if the subject has any post-dosing sample being positive in assay 5) and the pre-dosing sample was negative in assay 5) [this also includes the scenario of pre-dosing sample negative in assays 1) or 2) and therefore not tested in assay 5)].

Ferring Pharmaceuticals

^a The fold increase in titres will be determined by minimum significant ratio (MSR) experiments during assay validation and will be stated in the validation report and the clinical trial report.

Supersedes: 5.0 Page 63 of 103

Subjects with a treatment-induced anti-MENOUPUR antibody response (both with and without neutralizing capacity) will be followed until the response becomes negative or has returned to predosing level. These subjects will be called in for assessments at 2 months after the last post-dosing anti-MENOPUR antibody sampling. If required, further assessments will be made at 3, 4, 6, 9 and 12 months after the last post-dosing anti-MENOPUR antibody sampling. The assessments will be terminated when two consecutive assessments are negative or indicate that the pre-dosing level has been reached, with a maximum follow-up period of one year. The assessments will also be terminated if the subject commences a new treatment cycle with any gonadotropin preparation.

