1.2 Presentation of results

1.2.1 Presentation of descriptive results

Categorical data will be summarized, unless otherwise stated, using the frequency (n) and relative frequencies as a percentage (i.e.; 100*n/N).

Continuous data will be presented for observed values, unless otherwise stated, using the number of subjects (N), number of observations (n), mean and standard deviation (SD), median and interquartile range (IQR), and range (minimum to maximum).

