6.4 Safety Analysis Set

The safety analysis set comprises all treated subjects and is analyzed according to the actual treatment received.

7 Trial Population

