10.1 General Considerations

Safety summaries, unless otherwise stated, will be performed using the Safety analysis set and will be summarized as described in Section 1.2.1. Summaries will be made using all subjects, subjects in the <35 years age strata, and subject in the ≥35 years age strata.

All individual subject data will be listed per subject and treatment as observed including any derived values. Adverse event listings will also include an indicator of whether the adverse event occurred before, during, or after the COVID-19 pandemic trial hold.

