10.2.5 Treatment-induced Anti-MENOPUR Antibodies

The proportion of subjects with treatment-induced anti-MENOPUR antibodies as well as the proportion of subjects with treatment-induced anti-MENOPUR antibodies with neutralizing capacity will be tabulated. Within each treatment group, a 95% Clopper-Pearson confidence interval will be constructed for both the proportion of subjects with treatment-induced anti-MENOPUR antibodies and for the proportion of subjects with treatment-induced anti-MENOPUR antibodies with neutralizing capacity.

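### Read as written, the all-treated safety denominator keeps subjects without a post-dosing antibody result in the antibody proportions, so the Clopper-Pearson upper limits are slightly too low if anyone is untested

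*Protocol*

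**What the plan says.** - **Denominator.** Protocol 9.8.1 states: "For calculation of percentages, the denominator will be the total number of subjects in the respective treatment group", and goes on to specify the safety analysis set. SAP 6.4 defines that set: "The safety analysis set comprises all treated subjects and is analyzed according to the actual treatment received". No post-dosing sample is needed to belong to it.
- **SAP carry-over.** SAP 10.1: "Safety summaries, unless otherwise stated, will be performed using the Safety analysis set". SAP 1.2.1 gives categorical data as "relative frequencies as a percentage (i.e.; 100*n/N" without saying whether N means treated or tested. SAP section 13 declares a single departure from the protocol's planned analysis, center as a fixed effect, so the denominator rule is not withdrawn.
- **Antibody analysis.** Protocol 9.8.5 and SAP 10.2.5 tabulate the proportion with treatment-induced antibodies and the proportion with neutralizing capacity. The SAP adds: "Within each treatment group, a 95% Clopper-Pearson confidence interval will be constructed". Neither section names an antibody-evaluable subset or the n of the interval.
- **Definition of a response.** For subjects negative before dosing, Protocol 7.2.15 says "a treatment-induced anti-MENOPUR antibody response will be defined as any post-dosing sample being positive in the confirmatory assay". For subjects positive before dosing it requires a titer rise at a post-dosing assessment. Both routes need a post-dosing result.
- **Missing data.** Protocol 9.8.1: "Missing values will be treated as missing, except for causality, intensity, seriousness, and outcome of adverse events". SAP 10.1.1 repeats this. Antibody results are not among the exceptions.

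**The concern.** Two rules in the same protocol section pull apart. One leaves a missing antibody result missing. The other keeps the subject in the denominator, where she can only lower the proportion. The protocol's efficacy section avoids this: "Missing values will not be included in the calculation of percentages unless otherwise specified". The safety section has no such clause.

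Antibody frequency, overall and neutralizing, is a named secondary endpoint, and Protocol 1.3 describes the risk as very low. With few or no positives expected, the upper confidence limit carries most of the information. An exact interval has its stated coverage only if each subject counted in n could have been observed as positive. Untested subjects make n too large and the limit too favourable.

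**Working it through.** **Plan's own figure.** There is none to reproduce. The documents give no expected antibody rate, number of positives or fraction of missing antibody samples.

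**Inputs**
- Treated per arm N = 200: the planned number randomized per arm (Protocol 3.2), taking all as treated.
- Untested fraction m = 5% or 10%: assumed. The 5% equals the allowance in Protocol 9.1, but that allowance belongs to the primary endpoint and is used here only for illustration.
- Positives x = 0, 2, 4 or 10: assumed.

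**Step 1, point rate.** Let n = N(1 − m) be the number tested. The rate under Protocol 9.8.1 is x/N; the rate among those tested is x/n. Hence x/N = (1 − m) × x/n. With x = 4 and m = 5%: 4/200 = 2.00% against 4/190 = 2.11%, and 0.95 × 2.11% = 2.00%. With x = 0 both rates are 0%, so only the limit changes.

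**Step 2, upper limit.** The two-sided 95% Clopper-Pearson upper limit is the 0.975 quantile of a Beta(x + 1, n − x) distribution. For x = 0 this reduces to 1 − 0.025^(1/n):
- n = 200: 1 − 0.025^(1/200) = 1.83%
- n = 190: 1 − 0.025^(1/190) = 1.92%
- n = 180: 1 − 0.025^(1/180) = 2.03%

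**Step 3, results.** Rate (upper limit) for the same positives:

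| Positives | All treated, n = 200 | 5% untested, n = 190 | 10% untested, n = 180 |
|---|---|---|---|
| 0 | 0% (1.83%) | 0% (1.92%) | 0% (2.03%) |
| 2 | 1.00% (3.57%) | 1.05% (3.75%) | 1.11% (3.96%) |
| 4 | 2.00% (5.04%) | 2.11% (5.30%) | 2.22% (5.59%) |
| 10 | 5.00% (9.00%) | 5.26% (9.47%) | 5.56% (9.98%) |

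The understatement of the upper limit is 1.92 − 1.83 = 0.09 to 2.03 − 1.83 = 0.20 percentage points with no positives, and 5.30 − 5.04 = 0.26 to 5.59 − 5.04 = 0.55 points with four. If only 2% are untested (n = 196), the limits are 1.86% and 5.14%. If everyone is tested, the difference is zero.

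**The case against.** **The plan never says that untested subjects are negative.** True. A reader might infer a deliberate negative imputation, but both documents leave missing values missing; the negative count is only the arithmetic effect of the denominator rule. The n of the Clopper-Pearson interval is also inferred, from Protocol 9.8.1 with SAP 10.1, 1.2.1 and section 13, because SAP 10.2.5 does not state it. Table specifications sit in a separate document (SAP section 14) and may already use the number tested. This argues for writing the denominator down. It does not remove the protocol's stated rule.

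**Few subjects should be untested.** This largely stands. Post-dosing sampling is mandatory for exposed subjects (Protocol 6.4.2 and 6.5.2). It is to be scheduled after cycle cancellation (6.2.4) and for subjects who do not reach transfer (7.2.15), and the end-of-trial visit collects the second sample if it is outstanding (6.8). A subject must miss both windows to be untested. Some missingness remains possible: no data are collected after withdrawal of consent (4.4), and the COVID-19 amendment provides for contact by phone or other means when visits cannot be attended.

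**Wider consequences do not follow.** Neutralizing antibodies are listed among the trial stopping criteria, so a reader might infer that this rule weakens that safeguard. It does not: under Protocol 4.4 the Safety Management Team reviews each occurrence, and no rate or limit is used. A reader might also infer a biased comparison between arms, but SAP 10.2.5 plans within-arm intervals only, with no between-arm test, and nothing in the documents suggests different sampling completeness by arm. No decision threshold is tied to the upper limit, and individual data are to be listed.

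**Conclusion.** The point holds as a minor one. Read as written, the protocol's denominator leaves untested subjects in the antibody proportions, and the SAP makes no exception. The direction is certain under that reading: the upper limit is too low if any treated subject lacks an evaluable post-dosing result, and the point rate is too low if there is also at least one positive.

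For 0 to 4 positives and 5% to 10% untested, the upper limit is understated by about 0.1 to 0.55 percentage points. These sizes rest on assumed missing fractions and event counts, on 200 treated per arm, and on the inference that the interval uses the same denominator as the percentage. The primary analysis is not affected.

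**What to change.** In SAP 10.2.5 state, as an exception to Protocol 9.8.1, that both antibody proportions and their Clopper-Pearson intervals use treated subjects with at least one evaluable post-dosing antibody result. Classify them by the pre-dosing rules of Protocol 7.2.15, including its provision that a pre-dosing sample not run in the neutralizing assay, because it was negative in the screening or confirmatory assay, counts as negative there. Report by arm the number evaluable and the number not tested.

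The same kind of denominator could be considered for the markedly abnormal laboratory proportions in SAP 10.2.10.3. That is optional, since the size of the effect there has not been worked out.

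The cost is a short addition to the SAP and a line in the table, with no new data. The only downside is slightly higher, less favourable upper limits.
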